12.6 Adverse event reporting requirements for Millennium Pharmaceuticals Inc

NANT will notify Millennium Pharmaceuticals of all serious adverse events, both expected and unexpected, and copy all Medwatch forms and related correspondence to Millennium. Notification will be via Cognizant at the following contacts:

[contact]

Email: [contact]

12.7 Reporting Secondary AML/MDS

Within two weeks of an AML/MDS diagnosis or other secondary malignancy following treatment for cancer, submit the following to the NANT Operations Center:

- A completed NANT SAE Form
- A copy of the pathology report confirming the AML/MDS
- A copy of the cytogenetic report (if applicable)

The NANT Operations Center will submit the form and accompanying reports to [name] (IND Sponsor), Millennium Pharmaceuticals Inc, and to the FDA via MedWatch. All NANT institutions are to file the secondary malignancy reports with their Institutional Review Boards according to local institutional policy.

12.8 Procedures for Reporting Drug Exposure during Pregnancy and Birth Events

If a woman becomes pregnant or suspects that she is pregnant while participating in this study, she must inform the investigator immediately and must permanently discontinue study drug(s). All pregnancies and suspected pregnancies will be reported to Millennium Pharmacovigilance by the NANT Operations Office (see Section 12.4 for contact information) immediately. The pregnancy must be followed for the final pregnancy outcome (ie, delivery, still birth, miscarriage) and Millennium Pharmacovigilance will request this information from the investigator.

If a female partner of a male patient becomes pregnant during the male patient's participation in this study, this must be reported to Millennium Pharmacovigilance by the NANT Operations Office immediately (see Section 12.4 for contact information). Every effort should be made to follow the pregnancy for the final pregnancy outcome."

13.0 RECORDS AND REPORTING

See separate Data Forms Packet which includes the data submission schedule in the member section on the NANT web site (www.NANT.org)

The following are required to be submitted for all patients entered:

- Study case report forms including patient diaries to document administration of temozolamide and MLN8237, bone marrow reports (including aspirate and biopsy reports), urine catecholamine reports, and radiology reports (CT/MRI/MIBG/PET scans). These forms and reports are faxed to the NANT Operations Center at [contact] or sent by email as electronic files to [contact] at the end of each cycle of therapy.
- For **all** patients on study, CT/MRI and MIBG scans done as baseline tumor evaluation at study entry are required to be submitted into NANT PACS for central review (Bone marrow slides from study entry may also be requested at the discretion of the Operations Center).
- For all patients who report an overall response of CR, CRT-MRD, PR, Minor Response or who have SD for at least 4 cycles will submit all CT/MRI scans, MIBG scans, and bone marrow aspirate and biopsy slides done, during therapy and at end of protocol therapy for central review upon request by NANT Operations Center. Additional scans may also be requested by the NANT Operations Center to clarify response. Radiology scans are requested to be submitted via GRID, however CD/optical disk may also be sent to NANT Operations Center with patient identifiers removed (scans will be identified by NANT patient number/study number).
- For all patients, slides from bone marrow aspirates done at the time of study entry, during therapy and at end of therapy, are required to be submitted upon request to NANT Operations Center.

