11.0 RESPONSE CRITERIA VERSION 1.2

With Amendment #6, response criteria have changed to the following NANT Response Criteria version 1.2. The previous NANT Response Criteria versions 1.0 and 1.1 have been moved to Appendix VII and Appendix VIII, respectively, for reference. For all patients enrolling prior to Amendment #5, sites should continue to utilize version 1.0 to assess and report response. For all patients enrolling with Amendment #5 and after, sites will use version 1.2 to assess and report response. NANT central review of response will utilize version 1.2 for all patients.

Overall response will incorporate all three parameters: CT/MRI; MIBG (FDG-PET is substituted for MIBG non-avid tumors); and bone marrow response with response defined as outlined in Section 11.6. Response for each parameter and overall response will be reported by the treating site using the criteria below. However, the final statistical analysis of response will be defined by central review, using the same criteria below.

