11.3. Response Criteria for MIBG Avid Lesions

MIBG response will be graded using a modification of the Curie scoring scale (Eur J Cancer 1995;31A:256-261). The treating site will report the MIBG response using Curie, however the statistical endpoint of MIBG response will utilize the Curie score from the central reviewer.

MIBG scans will be scored for 10 regions; 9 anatomic regions for skeletal metastases, and a 10th region for any MIBG avid soft tissue disease.

Each of the 10 regions will be given a score of 0-3, as defined below.

Scoring of Skeletal Disease Regions 1 – 9	
Scoring	MIBG uptake
0	No MIBG uptake
1	1 focal lesion
2	> 1 focal lesion
3	> 50% of a region

The **absolute extension score** is obtained by adding the scores of all ten regions. The presence of a MIBG avid lesion, and NOT the “intensity” of MIBG-avidity, determines the scoring within a particular region.

REGIONS 1 – 9 / SKELETAL DISEASE: Cranio-facial disease is scored in Region 1, cervico-thoracic spine in Region 2, ribs / sternum / clavicles / scapula in Region 3, lumbar-sacral spine in Region 4, pelvis in Region 5, humeri in Region 6, distal upper extremities in Region 7, femurs in Region 8, and distal lower extremities in Region 9 (see figure below).

REGION 10 / SOFT TISSUE DISEASE: Soft tissue disease within the neck, chest or abdomen/pelvis is scored within Region 10. Examples of soft tissue lesions may include MIBG avid cervical, paraspinous, adrenal, renal, retroperitoneal, or hepatic masses.

SCORING SOFT TISSUE DISEASE: Score = 1 indicates an isolated soft tissue mass that encompasses < 50% of that region (chest or abdomen/pelvis). Score = 2 indicates > 1 soft tissue lesion in the neck, chest or abdomen/pelvis. A soft tissue score = 3 indicates MIBG avid soft tissue disease that encompasses > 50% of either the chest or abdomen/pelvis. (For example, a large adrenal mass in which the MIBG avidity encompasses > 50% of the abdomen/pelvis is scored a 3 for Region 10). Cervical soft tissue disease is included in the chest region.

If no MIBG-avid soft tissue lesions are present, then score 0 for Region 10.

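### Central review defines the response endpoint, but on-therapy scans are routinely called for only when the site reports a response, a minor response or SD of at least 4 cycles

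*Combined protocol and SAP*

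**What the plan says.** - **Endpoint.** Section 11.0 has sites report response but states that "the final statistical analysis of response will be defined by central review, using the same criteria below". It adds that "NANT central review of response will utilize version 1.2 for all patients". Section 11.3 says that "the statistical endpoint of MIBG response will utilize the Curie score from the central reviewer".
- **Baseline material.** Section 13.0 covers every patient: "CT/MRI and MIBG scans done as baseline tumor evaluation at study entry are required to be submitted into NANT PACS for central review".
- **On-therapy material.** Section 13.0 then sets a trigger. Patients with a site-reported CR, CR-MRD, PR or minor response, and those "who have SD for at least 4 cycles will submit all CT/MRI scans", along with MIBG scans and marrow slides, done "during therapy and at end of protocol therapy for central review upon request by NANT Operations Center".
- **Other routes in section 13.0.** The Operations Center may ask for further scans to clarify response. Marrow aspirate slides can be requested for any patient.
- **Who is a responder.** Section 10.2.2 counts CR, VGPR and PR as response. Stable disease, mixed response, progression and inevaluable are non-response, and the initial analysis includes all eligible patients who receive study therapy. Section 10.6.2 analyses best response.
- **Timing and size.** Section 7.3 schedules evaluations in cycles 2, 4, 8 and every 4 cycles after that. Section 10.4 enrols at most 20 phase 2 patients.

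Neither section 10.2.2 nor section 10.6.2 says how a patient with no central on-therapy read is classified in the final analysis.

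**The concern.** Whether a patient's on-therapy scans reach the central reader depends on the outcome that the central reader is meant to judge. Site-called PD, SD under 4 cycles and not-evaluable patients are outside the routine submission rule. For them the endpoint is in effect the site's grade, although section 11.0 describes it as central.

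A concrete case: the site grades SD at cycle 2 and PD at cycle 4. This patient meets no trigger. If a central reader would have graded PR at cycle 2, the patient's best response is PR, but that is not recognised unless someone happens to request the scans. The margin can be narrow. Section 11.3 grades an MIBG relative score from 0.1 to 0.5 as PR. With a baseline Curie score of 4, a follow-up score of 2 gives 2/4 = 0.50 (PR) and a score of 3 gives 3/4 = 0.75 (SD).

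At stake is the primary phase 2 estimate, the objective response rate in at most 20 patients.

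**Working it through.** **The plan's own figures.** Section 10.4 gives a 90% chance of at least 1 response in 14 at a true rate of 15%: 1 − 0.85^14 = 0.897, which agrees. Its bound of 0.24 on the 95% confidence interval half-width also holds: an exact interval that allows for the stop at 0 of 14 has its largest half-width, 0.228, at 10 of 20. Neither figure is in dispute; they give the scale.

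**Direction against full central review.** Compare the section 13.0 rule with central reading of everyone, and assume that all listed patients are read under both.
1. Every unlisted patient is a site-called non-responder or not evaluable, so is counted as a non-responder if unread.
2. Reading such a patient can leave the grade as it is or upgrade it. It cannot remove a response.
3. The denominator is the same, because section 10.2.2 does not define it by central review.

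So the rate under the rule is equal to or lower than the rate under full review.

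**Direction against the site-read rate.** Take 20 patients and the mix that section 2.2 reports for irinotecan and temozolomide (16% response, 47% SD), assumed to apply here:
- site responders: 0.16 × 20 = 3.2
- SD: 0.47 × 20 = 9.4
- other: 20 − 3.2 − 9.4 = 7.4

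Let f be the share of the SD group that is minor response or SD of at least 4 cycles, d the chance that a site response is downgraded, and u the chance that a non-response is upgraded. The documents give none of these. Revisions balance when 3.2 × d = 9.4f × u, that is u/d = 3.2/(9.4f). Unread patients number 16.8 − 9.4f. The shortfall against full review is unread × u / 20.

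| f | Reviewed non-responders (9.4f) | Unread | Break-even u/d | Shortfall at u = 5-10%, points | Same, if only short SD can be upgraded: 9.4(1 − f) × u / 20 |
|---|---|---|---|---|---|
| 0.25 | 2.35 | 14.45 | 1.36 | 3.6-7.2 | 1.8-3.5 |
| 0.50 | 4.70 | 12.10 | 0.68 | 3.0-6.1 | 1.2-2.4 |
| 0.75 | 7.05 | 9.75 | 0.45 | 2.4-4.9 | 0.6-1.2 |
| 1.00 | 9.40 | 7.40 | 0.34 | 1.9-3.7 | 0 |

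Two examples show that the net movement from the site rate of 16% can go either way:
- f = 0.50, d = 0.20, u = 0.05: (3.2 × 0.80 + 4.70 × 0.05)/20 = 14.0%. Full review with the same u: (2.56 + 16.8 × 0.05)/20 = 17.0%.
- f = 0.75, d = 0.10, u = 0.10: (3.2 × 0.90 + 7.05 × 0.10)/20 = 17.9%. Full review: (2.88 + 16.8 × 0.10)/20 = 22.8%.

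**Simple illustration.** With 8 of 20 unread and u = 5-10%: 8 × 0.05/20 = 2 points and 8 × 0.10/20 = 4 points.

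**The case against.** The strongest case against the point has five parts.

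1. **Review is targeted sensibly.** Minor responses and SD of at least 4 cycles are non-responders under section 10.2.2, yet they are reviewed. They are plausibly the non-responders nearest to PR. This stands. A reader might infer that central review can mostly only lower the rate; the documents do not support that, because these patients can be upgraded and may outnumber the site responders.
2. **The other patients are not shut out.** Extra scans may be requested for any patient, and section 13.0 refers to a separate data forms packet that is not part of these documents. So it would be wrong to say that their scans are never read. But the request is discretionary with no stated trigger, and the slides available for every patient are aspirates only. Section 11.6.3 requires PR on CT/MRI or on MIBG (or FDG-PET) for an overall PR, so slides alone cannot establish one.
3. **The all-patients sentence in section 11.0 concerns the criteria version.** That is a fair reading. The point does not need that sentence; the statement that central review defines the final analysis is enough.
4. **Site-called PD is rarely a missed PR.** On CT it would mean moving from at least a 20% increase, or a new lesion, to at least a 30% decrease with no new lesion. Section 11.6.4 also allows PD by clinical assessment, with no imaging to read. This stands and lowers the likely size.
5. **The effect is small beside the sampling error.** 2-4 points is little against a half-width of up to 24 points. This stands, and is why the point is only an improvement.

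**Conclusion.** The point holds as a cheap improvement. Central review defines the final response analysis, but its routine on-therapy input is selected by the site's outcome call. Relative to full central review the response rate can only be equal or lower, provided that listed patients are in fact read and unread patients count as non-responders. Relative to the site-read rate the net direction is not fixed.

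The size cannot be calculated from the documents. It is about 2-4 points if 8 of 20 patients are unread with a 5-10% chance of an upgrade, both assumed, and probably less because site-called PD is unlikely to be upgraded. The larger values in the table need site-called PD to be upgraded as often as SD.

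A reader might also infer that one missed response could wrongly stop the trial after stage 1. The documents do not support this: section 11.0 ties central review to the final analysis, and section 10.4 does not say that the stage 1 count uses central reads.

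**What to change.** In section 13.0, for the phase 2 portion, require every treated patient's scheduled on-therapy and end-of-therapy CT/MRI and MIBG (or FDG-PET) scans and marrow slides to be submitted, whatever response the site reports, and read by the existing central reviewers. The endpoint in section 11.0 is then central for all of at most 20 patients.

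In section 10.6.2, report the site-read rate beside the central rate. State how many patients could not be read centrally, such as those with PD by clinical assessment without imaging, and count them as non-responders. The site-read rate alone would not be enough: it shows disagreement but recovers no missed response.

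The cost is extra submission and reading time for the patients now left out. That is 8 of 20 on the simple assumption, and about 7 to 14 of 20 on the section 2.2 mix, depending on how many SD patients already qualify. Many of them would have only one or two evaluations. No new reader, procedure or patient is needed.

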APPENDIX I: PERFORMANCE STATUS SCALES/SCORES

Performance Status Criteria					
ECOG (Zubrod)		Karnofsky		Lansky*	
Score	Description	Score	Description	Score	Description
0	Fully active, able to carry on all pre-disease performance without restriction.	100	Normal, no complaints, no evidence of disease	100	Fully active, normal.
		90	Able to carry on normal activity, minor signs or symptoms of disease.	90	Minor restrictions in physically strenuous activity.
1	Restricted in physically strenuous activity but ambulatory and able to carry out work of a light or sedentary nature, e.g., light housework, office work.	80	Normal activity with effort; some signs or symptoms of disease.	80	Active, but tires more quickly
		70	Cares for self, unable to carry on normal activity or do active work.	70	Both greater restriction of and less time spent in play activity.
2	Ambulatory and capable of all self-care but unable to carry out any work activities. Up and about more than 50% of waking hours	60	Required occasional assistance, but is able to care for most of his/her needs.	60	Up and around, but minimal active play; keeps busy with quieter activities.
		50	Requires considerable assistance and frequent medical care.	50	Gets dressed, but lies around much of the day; no active play, able to participate in all quiet play and activities.
3	Capable of only limited self-care, confined to bed or chair more than 50% of waking hours.	40	Disabled, requires special care and assistance.	40	Mostly in bed; participates in quiet activities.
		30	Severely disabled, hospitalization indicated. Death not imminent.	30	In bed; needs assistance even for quiet play.
4	Completely disabled. Cannot carry on any self-care. Totally confined to bed or chair.	20	Very sick, hospitalization indicated. Death not imminent.	20	Often sleeping; play entirely limited to very passive activities.
		10	Moribund, fatal processes progressing rapidly.	10	No play; does not get out of bed.

*The conversion of the Lansky to ECOG scales is intended for NCI reporting purposes only.

APPENDIX II. MLN8237 DOSING TABLES FOR PATIENTS RECEIVING ENTERIC COATED TABLETS

Patients receiving the oral solution should have their dose rounded according to section 4.2.1.

(Note that the surface area divisions change at each dose level for rounding purposes)

DOSE LEVEL -1B: 30 MG/M²/DOSE

Body Surface Area (m²)	Dose Level -1 (30 mg/m²)
0.38-0.49	10 mg
0.5-0.83	20 mg
0.84-1.16	30 mg
1.17-1.49	40 mg
1.5-1.83	50 mg
> 1.84	60 mg

DOSE LEVELS 1 AND 1B: 45 MG/M²/DOSE

Body Surface Area (m²)	Dose Level 1 (45 mg/m²)
0.38-0.55	20 mg
0.56-0.77	30 mg
0.78-0.99	40 mg
1.0-1.22	50 mg
1.23-1.44	60 mg
1.45-1.66	70 mg
1.67-1.88	80 mg
> 1.89	90 mg

DOSE LEVEL 2B: 60 MG/M²/DOSE

Body Surface Area (m²)	Dose Level 2 (60 mg/m²)
0.38-0.41	20 mg
0.42-0.58	30 mg
0.59-0.74	40 mg
0.75-0.91	50 mg
0.92-1.08	60 mg
1.09-1.24	70 mg
1.25-1.41	80 mg
1.42-1.58	90 mg
1.59-1.74	100 mg
1.75-1.91	110 mg
> 1.92	120 mg

DOSE LEVEL 3B: 80 MG/M²/DOSE

Body Surface Area (m²)	Dose Level 3 (80 mg/m²)
0.38-0.43	30 mg
0.44-0.56	40 mg
0.57-0.68	50 mg
0.69-0.81	60 mg
0.82-0.93	70 mg
0.94-1.06	80 mg
1.07-1.18	90 mg
1.19-1.31	100 mg
1.32-1.43	110 mg
1.44-1.56	120 mg
1.57-1.68	130 mg
1.69-1.81	140 mg
1.82-1.93	150 mg
> 1.94	160 mg

APPENDIX IIIA.TEMOZOLOMIDE DOSING TABLE FOR INITIAL DOSING WITH 100 MG/M²

BSA (m ²)	Calculated daily dose (mg)	Administered daily dose (mg)
0.1-0.49*	3.3 mg/kg*	3.3 mg/kg*
0.50-0.52	50-52	50
0.53-0.57	53-57	55
0.58-0.62	58-62	60
0.63-0.67	63-67	65
0.68-0.72	68-72	70
0.73-0.77	73-77	75
0.78-0.82	78-82	80
0.83-0.87	83-87	85
0.88-0.92	88-92	90
0.93-0.97	93-97	95
0.98-1.0	98-100	100
1.0-1.05	100-105	105
1.06-1.14	106-114	110
1.15-1.24	115-124	120
1.25-1.34	125-134	130
1.35-1.44	135-144	140
1.45-1.54	145-154	150
1.55-1.64	155-164	160
1.65-1.74	165-174	170
1.75-1.84	175-184	180
1.85-1.94	185-194	190
≥ 1.95	195-2.0	200

*Dosing for patients under BSA 0.5 m² is by mg/kg, rounded to the nearest 5 mg

APPENDIX IIIB.TEMOZOLOMIDE DOSING TABLE FOR 75 MG/M² IF DOSE REDUCTION NEEDED

BSA (m ²)	Calculated daily dose (mg)	Administered daily dose (mg)
0.1-0.49*	2.5 mg/kg*	2.5 mg/kg*
0.50-0.56	37.5-42	40
0.57-0.63	42.75-47.25	45
0.64-0.69	48-51.75	50
0.70-0.76	52.5-57	55
0.77-0.83	57.75-62.25	60
0.84-0.89	63-66.75	65
0.90-0.96	67.5-72	70
0.97-1.03	72.75-77.25	75
1.04-1.09	78-81.75	80
1.10-1.16	82.5-87	85
1.17-1.23	87.75-92.25	90
1.24-1.29	93-96.75	95
1.30-1.36	97.5-102	100
1.37-1.43	102.75-107.25	105
1.44-1.49	108-111.75	110
1.50-1.56	112.5-117	115
1.57-1.63	117.75-122.25	120
1.64-1.69	123-126.75	125
1.70-1.76	127.5-132	130
1.77-1.83	132.75-137.25	135
1.84-1.89	138-141.75	140
1.90-1.96	142.5-147	145
≥ 1.97	≥ 147.75	150

*Dosing for patients under BSA 0.5 m² is by mg/kg, rounded to the nearest 5 mg

APPENDIX IV: FAMILY INSTRUCTIONS FOR ADMINISTRATION OF TEMOZOLOMIDE FOR PATIENTS WHO ARE UNABLE TO SWALLOW CAPSULES

Temozolomide is an oral cancer medicine that your child will be taking for treatment of his/her neuroblastoma. If your child is unable to swallow these capsules, you should use the following instructions to administer this medication safely.

- Temozolomide must be kept in a dark container
- Temozolomide should be taken at the same time everyday
- If your child requires nausea medicine it should be taken prior to the temozolomide
- If the dose of temozolomide is vomited later than 10 minutes after administration (which is unusual), do not repeat the dose
- If the person dispensing this medicine is pregnant or suspects she is pregnant, she should not dispense this medicine

Temozolomide is an anti-cancer agent, and so special precautions must be taken when handling this medicine. There is potential hazard to anyone who handles this medicine once the protective capsule is opened. Since your child is unable to swallow the capsule, you will be required to open the capsules and mix the contents of the capsule in apple sauce or apple juice. This process must be done according to the following guidelines to ensure safe administration of this medicine.

- Find a place that is as free of air flow as possible and is not an area where food is stored or prepared. The work surface should be covered with aluminum foil to reduce exposure to other members of the family.
- Temozolomide can be mixed in apple sauce or apple juice.
- Place the apple sauce or apple juice in a disposable container.
- Put on disposable gloves.
- Open each capsule and place the powder in a medicine cup.
- Add the whole contents of the medicine cup to either apple sauce or apple juice. The medicine will not dissolve completely if mixing in apple juice so have extra apple juice on hand so you can add it to any remaining powder in the bottom of the cup.
- If you need to use additional juice or apple sauce, remove your gloves before touching the main container then place new gloves on before adding the additional juice or apple sauce to the medicine. (You do not want to contaminate the main container with any powder that may be on your gloves.)
- Anything that comes into contact with the medicine must be disposable, such as the spoon used for mixing or eating the apple sauce.
- Once all of the medicine is taken throw away the following in the provided red bag: medicine cup, the container the medicine was mixed in, the cover for the work surface, gloves and anything else that has been in contact with the medicine.

Once a Five-day cycle of temozolomide is completed bring the red bag with you to the clinic so it can be disposed of properly.

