3.2.6 Ability to Swallow Pills

MLN8237 enteric coated tablets must be swallowed as whole tablets. Therefore, patients must be able to swallow pills to be eligible for the phase 2 portion of the study. Patients who are unable to swallow pills are eligible for the oral solution cohort.

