4.2.1 MLN8237

MLN8237 will be given once daily by mouth on days 1-7 of each 21-day cycle. On days 1-5, the dose should be given one hour prior to the start of the irinotecan infusion and at the same time as the dose of temozolomide on those days.

For patients in the phase 2 portion, the dose of MLN8237 will be 60 mg/m^2 (dose level 2B) using exclusively the enteric coated tablet. The dose should be rounded to the nearest 10 mg using the dosing table in Appendix II, with doses capped at 2 m^2 . Tablets should not be crushed, split, or chewed. The dose can be taken either on an empty stomach or with food on Days 6 and 7, though on Days 1-5 should be taken without food as the dose is taken at the same time as temozolomide (see below). If a patient vomits after taking a dose, it should not be re-dosed.

For patients in the oral solution cohort, the dose of MLN8237 will be based upon the dose level assigned at study entry. The oral solution may be administered by mouth, via nasogastric tube, or via gastrostomy tube. The calculated dose should be rounded down to the nearest 0.5 mg (0.1 mL of the 5 mg/mL oral solution). The dose must be taken on an empty stomach (NPO two hours before and one hour after each dose). If a patient vomits after taking a dose, it should not be re-dosed.

EXAMPLES

- Assigned dose 45 mg/m^2 and BSA 0.83 m^2 → Calculated dose = 37.35 mg → Round down to 37.0 mg → Administer 7.4 mL of 5 mg/mL solution
- Assigned dose 45 mg/m^2 and BSA 0.84 m^2 → Calculated dose = 37.8 mg → Round down to 37.5 mg → Administer 7.5 mL of 5 mg/mL solution

For both formulations of the drug, systemic antacids (both H2 receptor antagonists and proton pump inhibitors) may alter MLN8237 exposure and should be avoided during MLN8237 treatment. Locally-acting antacids should not be taken simultaneously with MLN8237 but antacids can be given up to 2 hours prior or 2 hours following MLN8237 administration.

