4.2.2 Temozolomide

Temozolomide will be given at a dose of $100 \text{ mg/m}^2/\text{dose}$ orally on days 1-5 of each 21-day cycle. The dose for patients $< 0.5 \text{ m}^2$ is $3.3 \text{ mg/kg}/\text{dose}$, respectively. The dose should be rounded based on the dosing table in Appendix III, with doses capped at 2 m^2 . The dose should be given one hour prior to irinotecan infusion and should be given at the same time as the dose of MLN8237. The dose should be taken on an empty stomach (NPO one hour before and one hour after each dose). If a patient vomits within 20 minutes of taking a dose, the dose should be re-dosed. If a patient vomits more than 20 minutes from taking a dose, the dose should not be re-dosed.

For patients unable to swallow pills, temozolomide capsules can be opened and drug administered using the instructions given in Appendix IV. Alternatively, an extemporaneous suspension can be prepared according to the instructions given in section 6.3.

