The phase 1 and 2 portions of the study utilize a 10 mg enteric coated tablet. In addition to the active drug, the tablets also contain sodium bicarbonate, sodium lauryl sulfate, povidone, microcrystalline cellulose, croscarmellose sodium, and sodium stearyl fumarate. The tablets are packaged in high-density polyethylene (HDPE) bottles with a child resistant cap. Each bottle contains 10 tablets. Tablets should remain in the provided bottle until dispensing. The exact number of tablets per cycle can be counted and dispensed in prescription HDPE bottles. The tablets are stored at controlled room temperature of 20°-25°C (68°-77°F) with excursions permitted from 15°-30°C (59°-86°F).

The oral solution cohort utilizes a 5 mg/mL oral solution. In addition to the active drug, the solution also contains sodium bicarbonate, polyethylene glycol 400, propylene glycol, glycerol, acesulfame potassium, bubble gum flavor, and purified water. The solution is provided in 60 mL amber polyethylene terephthalate bottles with a child resistant cap. The solution should remain in the provided bottle until ready for dispensing in the clinic or at home. The investigational pharmacist may draw up a patient's dose on the day a patient receives therapy at the study center, but should not draw-up the full 7-day course of therapy into prefilled syringes and dispense that supply to the patient. Instead, parents/guardians will be instructed to draw up each dose at home prior to administration. The bottles are to be stored at controlled room temperature of 20°-25°C (68°-77°F) with excursions permitted from 15°-30°C (59°-86°F). Patients are to start each cycle of therapy with a new supply of bottles, rather than using any remaining solution from previous cycles.

Guidelines for Administration: See also Treatment and Dose Modification in Section 4.0.

MLN8237 is a cytotoxic anticancer drug and should be handled according to published guidelines for handling cytotoxic drugs. Tablets should not be crushed or manipulated in any way.

The oral solution formulation of the drug must be given on an empty stomach, at least one hour before and two hours after food or drink except water.

The tablet must be swallowed whole, but may be given with or without food.

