10.5 Statistical Rules for Oral Solution Cohort

Up to 6 patients evaluable for dose escalation consideration (section 10.2.1) will be enrolled at the starting dose level for this cohort (dose level 1B = one dose level below the phase 2 dose obtained with enteric coated tablets), following the rolling-six rules in section 10.3. After enrollment to this dose level is complete, the toxicity and pharmacokinetic parameters will be assessed by the study committee.

If dose de-escalation is indicated based upon toxicity at dose level 1B, this will occur following the rolling-six rules in section 10.3 and will occur independent of pharmacokinetic results.

If dose escalation appears feasible based upon toxicity at dose level 1B, this will occur following the rolling-six rules in section 10.3 only if the study committee determines that MLN8237 exposures are below predicted levels at dose level 1B. This provision is in place since dose level 2B with the oral solution is predicted to be comparable to dose level 3B with the tablet formulation and that dose level was not tolerable in the phase 1 portion of the study.

Once the MTD with the oral solution has been determined, the study committee will assess the pharmacokinetic parameters to determine if enrollment of up to additional 6 patients at the MTD will be needed to better characterize the pharmacokinetic profile of the oral solution. Interpatient variability and comparison with exposures obtained with oral solution and enteric coated tablets will be used to drive this determination.

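### For oral solution patients, giving temozolomide from opened capsules in apple sauce or juice contradicts the fasting rule for MLN8237 solution taken at the same time, and the protocol text neither fixes nor records the route used on the Day 4 PK dose.

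*Combined protocol and SAP*

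**What the plan says.** **Who is in the cohort.** Section 3.2.6: "Patients who are unable to swallow pills are eligible for the oral solution cohort". Whole temozolomide capsules are therefore not an option for them.

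**MLN8237 solution.** Section 4.2.1: "The dose must be taken on an empty stomach (NPO two hours before and one hour after each dose". Section 6.1 says that it "must be given on an empty stomach, at least one hour before and two hours after food or drink except water". On Days 1-5 Section 4.2.1 places the dose "at the same time as the dose of temozolomide on those days".

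**Temozolomide.** Section 4.2.2 has its own empty-stomach rule, with an hour of fasting on each side of the dose. It then gives two routes to patients who cannot swallow pills. The first is "For patients unable to swallow pills, temozolomide capsules can be opened and drug administered using the instructions given in Appendix IV"; the second is an extemporaneous suspension prepared as in Section 6.3. Section 6.3 describes the suspension first and offers opened capsules in apple sauce or juice as the alternative.

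**The family handout (Appendix IV).** It tells the family "you will be required to open the capsules and mix the contents of the capsule in apple sauce or apple juice". It advises keeping more juice ready for leftover powder, sets no volume limit, and mentions neither fasting nor the suspension.

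**Use of the data.** Section 8.1.2 takes the MLN8237 PK profile on Day 4 of cycle 1. Section 10.5 allows escalation from 1B to 2B "only if the study committee determines that MLN8237 exposures are below predicted levels at dose level 1B". Section 10.8 compares tablet and solution parameters qualitatively.

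**The concern.** Three instructions meet on Days 1-5 for the same patient: take both drugs together, take MLN8237 solution fasting, and (in the handout) take temozolomide in apple sauce or juice. They cannot all be followed.

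Fasting is a deliberate rule here. Sections 4.2 and 4.2.1 relax it for tablets but keep it for the solution. Even for tablets, Section 4.2.1 rules out food on Days 1-5 because temozolomide is taken at the same moment. The shared dosing time was thus considered for tablets, but the handout used in the solution cohort was not brought into line.

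The statistical interest lies in the Day 4 profile. It feeds a dose-escalation decision and the formulation comparison under Aim 1.3. If some profiles come from doses taken with sauce or juice and others from fasted doses, and the difference is not recorded, the committee cannot separate the formulation from the conditions of administration.

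**Working it through.** The main check sets the instructions side by side for an oral solution patient on Days 1-5.

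| Instruction | Suspension route | Opened-capsule route |
|---|---|---|
| MLN8237 and temozolomide together (4.2.1, 4.2.2) | can be met | can be met |
| MLN8237 solution fasting (4.2.1, 6.1) | no sauce or juice called for | contradicted |
| Temozolomide on an empty stomach (4.2.2) | no sauce or juice called for | contradicted |
| Appendix IV handout | not mentioned | worded as required |

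The conflict therefore belongs to one of two permitted routes, and that route is the only one the handout shows to families.

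**Do the two MLN8237 fasting windows agree?** Yes. Section 6.1 gives "at least one hour before and two hours after food or drink except water". A dose at least one hour before food means nothing for one hour afterwards; a dose at least two hours after food means nothing for two hours beforehand. That is the window in Section 4.2.1.

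**Extent.** MLN8237 is given on Days 1-7 and temozolomide on Days 1-5, so co-dosing covers 5 of 7 MLN8237 doses per cycle. Day 4 is one of them. The Day 4 pre-dose sample also reflects the Day 1-3 doses, which are co-dosing days too.

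**What is recorded.** Section 8.1.4 puts the patient number, a drug label, the protocol number, date and time on the PK tube. Section 7.1 lists a diary, and Section 13.0 says that diaries document administration of both oral drugs. Neither the vehicle nor the time of last food or drink is called for.

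**The prediction behind the exposure decision.** Section 2.12 gives an adult AUC ratio, solution to powder-in-capsule, of 1.26 (90% CI 1.09-1.47), and calls the capsule similar in bioavailability to the tablet.

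- Solution 2B: 60 × 1.26 = 75.6 mg/m² capsule-equivalent (60 × 1.09 = 65.4 to 60 × 1.47 = 88.2), against 80 at tablet 3B. This agrees with Section 10.5, which calls the two comparable.
- Solution 1B: 45 × 1.26 = 56.7 (49.1 to 66.2), against 60 at tablet 2B.
- Using the tablet-to-capsule ratio of 90% in Section 2.6: 75.6 / 0.90 = 84.0 and 56.7 / 0.90 = 63.0.

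**Sensitivity to an assumed vehicle effect.** The documents give none, so the range below is purely illustrative. It applies to a patient on the opened-capsule route at 1B (56.7 × factor).

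| Assumed change in AUC | -30% | -20% | -10% | 0 | +10% | +20% | +30% |
|---|---|---|---|---|---|---|---|
| Capsule-equivalent, mg/m² | 39.7 | 45.4 | 51.0 | 56.7 | 62.4 | 68.0 | 73.7 |

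As a yardstick, a fall of 1 − 1.09/1.26 = 13.5% would take the ratio to its lower 90% limit, and a rise of 1.47/1.26 − 1 = 16.7% to its upper limit. Neither limit is a protocol threshold; Section 10.5 sets none. A fall could make exposure look low and favour escalation; a rise could block it. The cohort average would move less, depending on how many patients use this route, which the documents do not say.

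**The case against.** The strongest reply is that a site can comply today. Sections 4.2.2 and 6.3 offer the suspension, and the opened-capsule wording in the body of the protocol is permissive. This stands, and it limits the point to patients using opened capsules. It does not cure a handout that presents sauce or juice as required and omits the alternative.

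Second, Section 8.1.2 tells patients to hold the Day 4 and Day 5 MLN8237 doses until instructed at the treating site, so the PK dose is not left to the family. This also stands. But nothing there says how temozolomide is to be given on those days, and site control does not extend to Days 1-3.

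Third, the diary and PK forms sit in a separate Data Forms Packet that is not part of these documents. They may capture the vehicle. The point can only be that the protocol text does not require it.

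Fourth, escalation also needs acceptable toxicity under the rolling-six rules and a committee judgement, and the formulation comparison is qualitative. So a vehicle effect would be one input among several.

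A reader might go further and infer that the exposure decision rests on a fasted condition which the handout breaks. The documents do not support that. Section 10.5 states no prandial condition for the predicted levels, and Section 2.12 does not give one for the adult study. The remark in Section 6.3 that food reduces absorption concerns temozolomide, not MLN8237.

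**Conclusion.** The contradiction is in the current text and should be removed. For oral solution patients using opened capsules, the handout conflicts with the fasting rule for MLN8237 solution and with temozolomide's own empty-stomach rule, on 5 of 7 MLN8237 doses per cycle. Because Day 4 is a co-dosing day, and the protocol text neither fixes the route nor requires it to be recorded, route is an uncontrolled source of variation in the exposures that Sections 10.5 and 10.8 use. Its size and direction are unknown.

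Two further inferences are not supported. One is that all of the planned 6-18 patients are affected: the suspension is available, and the documents do not say how many would use each route. The other is that any particular share of the 1B profiles would be non-fasted. Section 10.5 caps patients evaluable for dose escalation at 6 for that level, but no figure for route use is given.

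The conclusion assumes that apple sauce and apple juice count as food or drink under Section 6.1, which is its plain meaning. No sample size, power or error rate changes.

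**What to change.** 1. Reconcile Sections 4.2.1, 4.2.2, 6.1, 6.3 and Appendix IV so that one consistent set of instructions applies when both drugs are taken together on Days 1-5, and correct the handout to match, including how it presents the suspension option. No view is taken here on which administration rule is right.
2. For the Day 4 PK dose, record the temozolomide route (suspension, or opened capsule in sauce or juice) and the time of last food or drink.
3. Make these two items available to the study committee when it judges exposure under Section 10.5, and state the prandial condition that the predicted exposure assumes, if it is known. With so few profiles this is descriptive context; a formal comparison by route would not be interpretable.

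The cost is a wording amendment, a reissued handout and two form fields, with no added visits or samples.
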